5.1 Overview

The LLINs will be distributed according to detailed national guidelines, which build on prior experience from a similar net distribution campaigns carried out in 2013-2014 and 2017-18, incorporated guidance for LLIN distribution in the context of COVID-19, and lessons from food distribution during COVID-19. The overall goal of the 2020 LLIN distribution campaign is to reduce malaria morbidity and mortality in Uganda by achieving universal coverage with LLINs, aiming to ensure that: (1) 85% of the targeted population has access to a LLIN, and (2) 85% of LLINs distributed are utilised. Members of the research team will engage with Uganda's national committees that are coordinating the LLIN universal coverage campaign, including the National Coordination Committee (NCC), which will be responsible for overall coordination and oversight of campaign planning, implementation, and engagement with political and traditional authorities, the operations sub-committee, the logistics sub-committee and the advocacy, communication and social mobilisation sub-committee. All LLINs procured for the campaign will be stored centrally in at the National Medical Stores warehouses in Entebbe and will be distributed across the country in waves. The 32 districts selected for this study are included in Waves 3-5 and are scheduled to receive nets from October 2020 to February 2021, although the timelines are subject to change depending on procurement and importation of the LLINs. The research team will work closely with the NCC and other stakeholders to ensure that the nets are allocated per the randomisation scheme.

5.2 Household registration and LLIN distribution

A key aspect of the distribution will be to ensure that the community members receive the correct number of LLINs. The LLINs will be stored centrally at the National Medical Stores warehouses in Entebbe, and then transferred from the central location to sub-county stores, and then onward to the household. A 'door to door' model of LLIN delivery will be applied with registration and LLIN distribution carried out concurrently. The processes will be handled by a multidisciplinary team, comprised of 5 individuals including: village health team member (VHT)/data clerk, security personnel, Local Council 1 (LC1), and two LLIN carriers. On average, there will be two teams per village for rural settings and four teams per village for urban settings, including towns and municipalities.

The Electronic Data Management Information System (EDMIS) will be used for data management including the following: (1) collection of household-level registration data; (2) establishment of household LLIN need; (3) allocation of number of LLINs for each household; and (4) assignment of household Chalk ID. The VHTs/data clerk will interview the head of household if available, or another adult resident, using the EDMIS electronic system. Information collected will include: (1) name of the household head; (2) National ID number of the head of household; (3) number of residents; (4) number of children under 5 years of age; (5) number of pregnant women; (6) sleeping places available; and (7) the telephone number for the household (if available). The EDMIS electronic system will then generate the Chalk ID and allocate LLINs automatically for each household based on the registration data. The assigned Chalk ID will be written on the household and the allocated LLINs issued to the head of household, or another adult resident,

immediately. The household LLIN distribution will be based on household population with one LLIN distributed for every two people living in the household. The recipient of the LLINs will acknowledge receipt using an appropriate method.

5.3 Social behaviour change communication

The NMCD and other stakeholders will take the lead on Social Behaviour Change Communication (SBCC). The UMIS 2018 showed that over 43% of the LLINs in the country were not being used. Thus, a comprehensive SBCC campaign is planned to increase LLIN utilization, with the campaign branded '*under the net 2020-2022*'. SBCC activities will use digital and other platforms, similar to those used for the COVID-19 response, including the following: (1) LLIN launch on television and radio; (2) regional advocacy meetings on Zoom; (3) mass media platforms (for advertisements, mini skits, DJ mentions, radio spots, interactive talks); (4) social media platforms; (5) VHTs; (6) operation hotlines and toll-free call centres; (7) community mobilisation (megaphones); and (8) use of appropriate information, education, and communication materials. Communication will include messages about COVID-19, malaria, and use, care, repair and repurposing of LLINs.

6 Health facility surveillance

6.1 Data collection at MRCs

At each MRC, individual-level data from standardised registers for all patients presenting to the outpatient departments are entered into an Access database by on-site data entry officers. Primary data captured comes from the HMIS 002 standardised form (Appendix C) and includes location of residence (parish and village), age, gender, body temperature, history of subjective fever, type of malaria test done (rapid diagnostic test or microscopy), malaria diagnostic test results, any diagnoses given, and any treatments prescribed. The research team supports the sites with training, site support supervision, and buffer stock of laboratory supplies/consumables. We employ full-time regional surveillance coordinators based around the country, each supervising 8-10 MRCs. Team members based in Kampala include the programme manager, several study epidemiologists, a data manager, a laboratory manager, and administrative staff. Members of the core team visit the MRCs on a regular basis to provide refresher training and feedback, and to conduct laboratory quality control procedures. Core team members are also responsible for generating periodic reports, communicating with MOH officials and other key stakeholders, and conducting data analyses.

Table 2. Malaria reference centers

	District	MRC 1	Sub-county	Start date	MRC 2	Sub-county	Start date
1	Agago	Patongo HCIII	Patongo TC	Aug 14	Lira-Kato HCIII	Lapono	Oct 19
2	Amuru	Atiak HCIV	Atiak	Sep 14	Amuru HCIII	Amuru	Nov 19
3	Gulu	Awach HCIV	Awach	Aug 14	Pabwo HCIII	Bungatira	Oct 19
4	Kitgum	Namokora HCIV	Namokora	Sep 14	Kitgum Matidi HCIII	Kitgum Matidi	Nov 19
5	Koboko	Lobule HCIII	Lobule	Aug 18	Ayipe HCIII	Kuluba	Dec 19
6	Kole	Aboke HCIV	Aboke	Mar 14	Bala HCIII	Bala	Nov 19
7	Lamwo	Padibe HCIII	Padibe	Sep 14	Madi-Opei HCIII	Madi-Opei	Nov 19
8	Arua	Opia HCIII	Vurra	Sep 14	Cilio HCIII	Aii-vu	Dec 19
9	Nwoya	Koch Goma HCIV	Koch Goma	May 19	Alero HCIII	Alero	Jan 20
10	Omoro	Lalogi HCIV	Lalogi	Sep 14	Bobi HCIII	Bobi	Jan 20
11	Oyam	Anyeke HCIV	Oyam TC	Apr 14	Otwal HCIII	Otwal	Nov 19
12	Amuria	Asamuk HCIII	Asamuk	Nov 19	Morungatuny HCIII	Morungatuny	Dec 19
13	Bukedea	Bukedea HCIV	Bukedea	Nov 19	Kolir HCIII	Kolir	Nov 19
14	Kumi	Kamaca HCIII	Kanyum	Jan 20	Omatenga HCIII	Kumi	Nov 19
15	Apac	Teboke HCIII	Chegere	Feb 20	Akokoro HCIII	Akokoro	Feb 20
16	Busia	Lumino HCIII	Lumino	Jun 18	Busitema HCIII	Busitema	Mar 20
17	Jinja	Budondo HCIV	Budondo	Jan 20	Butagaya HCIII	Butagaya	Jan 20
18	Kapelebyong	Kapelebyong HCIV	Kapelebyong	Nov 19	Obalanga HCIII	Obalanga	Jan 20
19	Kwania	Aduku HCIV	Aduku TC	Oct 06	Apwori HCIII	Chawente	Nov 19
20	Kaliro	Bumanya HCIV	Bumanya	Dec 19	Nawaikoke HCIII	Nawaikoke	Feb 20
21	Luuka	Kiyunga HCIV	Luuka TC	Dec 19	Ikumbya HCIII	Ikumbya	Jan 20
22	Masindi	Bwijanga HCIV	Bwijanga	Dec 19	Kyatiri HCIII	Pakanyi	Dec 19
23	Mayuge	Buwaiswa HCIV	Buwaya	Jan 20	Kigandalo HCIV	Kigandalo	Feb 20
24	Kiryandongo	Diima HCIII	Mutunda	Mar 20	Kigumba HCIII	Kigumba	Feb 20
25	Buyende	Kidera HCIV	Kidera	Feb 20	Bugaya HCIII	Bugaya	Feb 20
26	Kaabong	Lokolia HCIV	Kaabong East	Jul 18	Kalapata HCIII	Kalapata	Feb 20
27	Hoima	Kigoroby HCIV	Kigoroby TC	Feb 18	Butema HCIII	Buhanika	Feb 20
28	Kibaale	Kibaale HCIV	Kibaale TC	May 18	Kyebando HCIII	Kyebando	Feb 20
29	Kyegegwa	Kakabara HCIII	Kakabara	Jan 20	Kyegegwa HCIV	Kyegegwa TC	Mar 20
30	Kayunga	Bbaale HCIV	Bbaale	Feb 18	Kangulumira HCIV	Kangulumira	Mar 20
31	Mubende	Kasambya HCIII	Kasambya	Dec 06	Kiyuni HCIII	Kiyuni	Feb 20
32	Moyo	Metu HCIII	Metu	Sept 20	Lefori HCIII	Lefori	Sept 20

Data will be collected for all patients presenting to the outpatient departments of the MRCs using the HMIS 002 outpatient register as the primary data source. Data from registers will be entered into customised electronic databases on site (Appendix D). Plans for management of the MRC data are described further in section 11.1.

7 Cross-sectional surveys

7.1 Overview

We propose to conduct cross-sectional community surveys at baseline (if resources are available), and at 12- and 24-months after LLIN distribution. The sampling frame for the community surveys will be generated from the enumeration of the MRC target areas (which will be conducted prior to the onset of the evaluation). Households will be randomly selected from each of the 64 clusters and screened until 50 households with at least one child aged 2-10 years are enrolled (a minimum of 3,1200 households). The cross-sectional community surveys will include two components: (1) a household survey targeting heads of households, and (2) a clinical survey of children aged 2-10 years. In 32 selected clusters (one per district), individuals of all ages from participating households will be enrolled into the clinical survey during the 12-month survey. The clinical surveys will include a finger-prick blood sample for thick blood smear, measurement of haemoglobin (in children < 5 years), and storage of blood on solid phase media such as filter paper.

7.2 Definitions

- **Household:** A household will be defined as any single permanent or semi-permanent dwelling structure acting as the primary residence for a person or group of people that generally cook and eat together. Some households may include members who sleep in other dwelling structures within the same compound, if the members are still dependent on the head of household in the main household.
- **Head of household:** The head of household is an adult person or persons who primarily make decisions for the general household (e.g. decisions on healthcare, income, etc.), including emancipated minors.
- **Household resident:** A resident within each household will be defined as a person who intends to have a sleeping place primarily at that location for a period of the next 6 months. This may include people who sleep in a separate house within the same compound, if they are still dependent on the head of household for decisions on finances and health care.

7.3 Household survey

7.3.1 Selection of households

Households from each of the 64 clusters will be randomly selected for participation in each of the community surveys. Within each cluster (MRC target area), households will be randomly sampled from a list of households enumerated by the study team, until 50 households with children aged 2-10 years are sampled per cluster.

7.3.2 Screening

When a household is identified, study personnel will briefly describe the purpose of the study to the head of the household (or their designate) in the appropriate language, and screen for eligibility (Appendix E).

The inclusion criteria are:

- 1 At least one adult aged 18 years or older present
- 2 Adult is a usual resident who slept in the sampled household on the night before the survey
- 3 Agreement of the adult resident to provide informed consent for the household survey

The exclusion criteria are:

- 1 Dwelling destroyed or not found

- 2 Household vacant
- 3 No adult resident home on more than 3 occasions

7.3.3 *Informed consent*

A detailed description of the informed consent procedures is provided in section 14.2. Briefly, study personnel will carry out the informed consent discussion with the head of the household (or their designate) in the appropriate language, and a translator will be used if necessary. The information sheets and consent forms will be available in English and the appropriate local languages. Following the consent discussion, the respondent will be asked by the study personnel to sign a written consent form to participate in a research study (consent form #1). If the respondent is unable to read or write, their fingerprint will substitute for a signature, and a signature from an impartial witness to the process will be obtained.

7.3.4 *Household survey questionnaire*

The household questionnaire (Appendix F) will be administered to the head of the household (or their designate), after obtaining their consent using a hand-held tablet computer. Information will be gathered on the characteristics of households and residents, proxy indicators of wealth including ownership of assets, and ownership and use of LLINs in the households, specifically focusing the nets distributed in the 2020-2021 LLIN campaign. The household survey questionnaire has been adapted from prior cross-sectional community surveys conducted in Uganda, including the national Malaria Indicator Surveys and the LLINeup trial [14, 38, 54, 55]. For the 12-month survey, we have added additional questions to assess knowledge, attitudes, and beliefs regarding COVID-19 and its effect on malaria care and control, as well as costs and treatment seeking behaviours for fever in the past two weeks.

7.4 Clinical survey

7.4.1 *Recruitment of participants*

Recruitment of households into the community survey will continue until 50 households with children aged 2-10 years are enrolled. All children aged 2-10 years from enrolled households who are present will be eligible for participation in the clinical survey. In 32 selected clusters (one per district), individuals of all ages from participating households will be enrolled into the clinical survey. Children will be identified from the household survey questionnaires. If an enrolled household has no children of appropriate age, they will be included in the household survey only, and will not take part in the clinical survey.

7.4.2 *Screening of participants*

At the end of the household questionnaire, study personnel will discuss the clinical survey with the head of the household (or their designate), if the household includes children age 2-10 years. Study personnel will briefly describe the purpose of the clinical survey in the appropriate language and will screen for eligibility criteria (Appendix G).

The inclusion criteria are:

- 1 Child aged 2-10 years (in all 64 sites) - In 32 selected clusters, individuals of all ages will be eligible
- 2 Usual resident who was present in the sampled household on the night before the survey
- 3 Agreement of adult or parent/guardian (of children) to provide informed consent
- 4 Agreement of child aged 8 years or older to provide assent

The exclusion criterion is:

- 1 Child not home on day of survey

7.4.3 *Informed consent*

A detailed description of the informed consent procedures is provided in section 14.2. Briefly, study personnel will carry out the informed consent discussion with the adult or parent(s) or guardian(s) of children. Informed consent will be conducted in the appropriate language and a translator will be used if necessary. Consent forms will be available in English and the local languages. Following the informed consent discussion, adults or parents/guardians will be asked by the study personnel to sign a written consent form to participate, or for their child(ren) to participate, in a research study (consent forms #2 & #6) and a second approved consent form for the future use of biological specimens obtained during the study (consent forms #3 & #7). Written assent to participate in the study will also be obtained from children aged 8 years and older at the time of screening (consent form #4). If an adult respondent or parent/guardian is unable to read or write, their fingerprint will substitute for a signature, and a signature from a witness to the informed consent procedures will be obtained.

7.4.4 *Clinical survey procedures*

The clinical surveys will be carried out by study personnel, including teams consisting of one clinician plus one research assistant. The surveys include measurement of temperature, subjective fever and a finger-prick blood sample for measurement of thick blood smear and haemoglobin (in children < 5 years), and storage of blood on solid phase media such as filter paper (Appendix H).

7.4.5 *Management of ill participants*

Participants who have a temperature of $\geq 38.0^{\circ}\text{C}$, or who report fever in the past 48 hours, will have an RDT performed by study personnel. Febrile participants will be treated with paracetamol as appropriate. Participants with a positive RDT and no evidence of severe malaria will be treated with artemether-lumefantrine (AL), which is the first-line recommended treatment for uncomplicated malaria in Uganda. Participants with a positive RDT and evidence of danger signs of severe disease will be referred for further evaluation and treatment. Any participant with other concerning clinical symptoms will also be referred to an appropriate health care facility at the discretion of the study personnel.

7.4.6 *Number and timing of surveys*

We anticipate carrying out at least 2 rounds of surveys (the 12- and 24-month post-distribution surveys at a minimum). Additional surveys (including a survey shortly after the distribution of LLINs) may be conducted, depending on the availability of funding. We currently have funding to conduct post-LLIN distribution surveys in 12 MRC target areas.

8 Entomology surveys

8.1 Overview

Funding permitting, entomology surveys will be carried out to collect mosquito specimens for estimating vector density and insecticide resistance monitoring. Collections will be carried out concurrently with the cross-sectional community surveys at 12- and 24- months. Mosquitoes will be collected from a sub-set of 10 households per cluster enrolled in the cross-sectional community survey. Female anopheles mosquitoes will be identified, and will be stored with silica gel in the field sites, prior to shipment to Kampala and onto LSTM for further analysis.

8.2 Recruitment and screening

In each cluster, 10 households will be selected randomly for the entomology survey from the list of households enrolled into the community household surveys. Study personnel will re-visit households on the list of randomly selected households to carry out the recruitment for the entomology survey. When a household on the selection list is identified, study personnel will briefly describe the purpose of the study in the appropriate language with the head of household (or their designate) and proceed with screening (Appendix I).

The inclusion criteria are:

- 1 At least one adult aged 18 years or older present
- 2 Adult is a usual resident who slept in the sampled household on the night before the survey
- 3 Agreement of the adult resident to provide informed consent for the entomology survey

The exclusion criteria are:

- 1 Dwelling destroyed or not found
- 2 Household vacant
- 3 No adult resident home on more than 3 occasions

8.3 Informed consent

A detailed description of the informed consent procedures is provided in section 13.2. Briefly, study personnel will conduct the informed consent discussion with the head of household (or their designate). Informed consent will be conducted in the appropriate language and a translator will be used if necessary. Consent forms will be available in English and the local languages (consent form #5). Following the informed consent discussion, the head of household (or their designate) will be asked to sign a written consent form for mosquitoes to be collected from their household. If the head of household (or their designate) is unable to read or write, their fingerprint will substitute for a signature, and a signature from a witness to the informed consent procedures will be obtained.

8.4 Entomology survey

Mosquitoes resting on interior surfaces will be collected by entomology technicians using Prokopack aspirators (John W. Hock Co., USA). Collections will be carried out just after dawn and continue until 10am. A standardised collection duration of ten minutes per house will be used, which is sufficient to mechanically aspirate mosquitoes from all resting surfaces in a typical house, while minimising disruption. Female anopheles mosquitoes will be identified phenotypically, enumerated, and stored on silica gel in the field, before being transported and refrigerated at a central laboratory in Kampala for potential future molecular analysis depending on the availability of resources. Mosquito samples may be shipped to the Liverpool School of Tropical Medicine (LSTM) to conduct molecular studies that cannot be conducted in Uganda.

9 LLIN durability assessment

9.1 Overview

Funding permitting, a sub-set of LLINs distributed during the 2020-2021 universal LLIN campaign will be withdrawn (and replaced) from households enrolled into the 12- and 24-month cross-sectional community surveys to assess net durability. During each community survey, 248 households (4 per cluster, 124 per study arm), will be randomly selected from the 64 clusters to participate in the net durability study and will have one net withdrawn for durability assessment. A sample of 124 nets (one per household) of two different types, PPF LLINs (Royal Guard) and PBO LLINs (PermaNet 3.0) will be collected, packaged, labelled and stored. Each net collected will be replaced by a new net of the same type set aside by the NMCP/Ministry of Health.

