4.1 Overview

We propose to conduct a rigorous, cluster-randomised trial to evaluate the impact of LLINs distributed in Uganda through the 2020 national universal coverage campaign. A cluster has been defined as the target area of an MRC. A total of 64 clusters have been included in the study, covering 32 high malaria burden districts in Uganda where IRS is not being implemented. Clusters have been randomised in a 1:1 ratio in blocks of two by district to receive one of two types of LLINs: (1) PPF LLINs (Royal Guard [n=32] and (2) PBO LLINs (PermaNet 3.0) [n=32] (Appendix A).

The intervention, including delivery of the LLINs and social and behaviour change communication (SBCC), will be led by the Ugandan NMCD and other stakeholders. Currently, LLINs are scheduled to be delivered in the study areas from November 2020 to March 2021. The evaluation will include health facility surveillance at the MRCs to generate continuous estimates of malaria incidence for each MRC target area, cross-sectional community surveys post-LLIN distribution (in a sub-set of clusters), and at 12- and 24-months after LLIN distribution (in all 64 clusters) to gather information on net survivorship and use, and parasite prevalence in children 2-10 years of age, entomology surveys, and assessment of net durability and efficacy. The primary outcome of the trial will be malaria incidence as estimated using the health facility surveillance. In 32 selected clusters (one per district), parasite prevalence and the seroprevalence of COVID-19 will be assessed during the 12-month survey in individuals of all ages from participating households.

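### Protocol 9.1 gives a net-durability sample that contradicts itself: 4 households in each of 64 clusters is 256 (128 per arm), not the stated 248 (124 per arm)

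*Protocol*

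**What the plan says.** Protocol 9.1 sets the sample for the durability work in one sentence: at each community survey, "248 households (4 per cluster, 124 per study arm), will be randomly selected from the 64 clusters". Each selected household "will have one net withdrawn for durability assessment". The next sentence repeats the per-arm number by net type: "A sample of 124 nets (one per household) of two different types", the types being the PPF net and the PBO net. Each net collected is to be replaced by a new one of the same type.

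The cluster count is not in doubt. Protocol 4.1 states: "A total of 64 clusters have been included in the study, covering 32 high malaria burden districts in Uganda". It gives the arms as "PPF LLINs (Royal Guard [n=32] and (2) PBO LLINs (PermaNet 3.0) [n=32". Table 1 in Protocol 4.3 shows 32 clusters for each net type, and Table 2 in Protocol 6.1 lists 32 districts with two reference centres each.

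The assessment is conditional. Protocol 9.1 opens: "Funding permitting, a sub-set of LLINs distributed during the 2020-2021 universal LLIN campaign will be withdrawn (and replaced". Protocol 13.1 lists net integrity and chemical content as secondary outcomes on the same condition. The SAP does not cover durability.

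**The concern.** The sentence gives a rule (four per cluster), a cluster count (64) and two totals (248 and 124), and the totals do not follow from the rule and the count. A field team cannot apply the rule in every cluster and also stop at the totals.

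This is the only sample size given for the durability work. Protocol 13.4.2 sizes the survey prevalence outcomes and describes the mosquito collections, but contains no durability calculation that could settle which number was intended. What is at stake is practical: how many nets are withdrawn in each cluster, how many replacements of each type must be on hand, and, if collection stops at 248, which clusters give fewer than four. No rule is given for that last choice.

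**Working it through.** **Inputs**
- Households per cluster per survey: 4 (Protocol 9.1)
- Nets per household: 1 (Protocol 9.1)
- Clusters: 64, with 32 per arm (Protocol 4.1; Table 1 in 4.3)
- Stated totals: 248 households, 124 per arm, 124 nets of each type (Protocol 9.1)

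**Attempt to reproduce the stated totals.** No power formula is given, so the only route is households per cluster × clusters × nets per household.
- Total: 4 × 64 × 1 = 256, against 248 stated
- Per arm: 4 × 32 × 1 = 128, against 124 stated

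Neither figure is reproduced.

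**Whether the totals agree with each other.** 2 × 124 = 248, so they do. The figure 124 also appears twice. A single mistyped digit is therefore an unlikely explanation.

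**What the totals would imply**
- At 4 per cluster: 248 / 4 = 62 clusters and 124 / 4 = 31 per arm
- Over all 64 clusters: 248 / 64 = 3.875 households per cluster

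**Other whole-number rules**
- 3 per cluster: 3 × 64 = 192 (96 per arm)
- 5 per cluster: 5 × 64 = 320 (160 per arm)

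No flat whole number per cluster gives 248. A loss of 8 / 256 = 3.125% would turn 256 into 248, but no loss allowance is stated.

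**Size of the gap**
- Per survey: 256 − 248 = 8 nets; 8 / 248 = 3.2% and 8 / 256 = 3.1%
- Per arm: 128 − 124 = 4 nets
- Over the 12- and 24-month surveys: 2 × 256 = 512 against 2 × 248 = 496, a difference of 16

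**Whether 248 can be reached with every cluster sampled.** Yes. With 4 nets from each of 56 clusters and 3 from each of 8, 56 × 4 + 8 × 3 = 224 + 24 = 248. If the 8 are both clusters in four districts, each arm has 28 × 4 + 4 × 3 = 112 + 12 = 124.

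**The case against.** The best case on the other side accepts the arithmetic and disputes its weight. The work is done only if funded, the SAP omits it, and no confirmatory test or power statement uses 248 or 124. Nothing in the documents makes 128 per arm the required number either: the slip could lie in the totals, in the per-cluster figure, or in an unstated restriction to 62 clusters. All of this stands. It limits the point to an inconsistency to be reconciled, without proof that 256 was intended.

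Two stronger readings are tempting, and the documents support neither.

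- A reader might infer that the shortfall breaks the district pairing of the randomisation. The planned durability analysis does not use that pairing. Protocol 13.5 specifies generalized estimating equations allowing for within-cluster correlation for net integrity, and an unpaired Wilcoxon rank sum test for chemical content. Nor does 248 force any pair to be broken: omitting both clusters of one district leaves 31 complete pairs, and the 56-and-8 split above keeps all 32.
- A reader might infer that a whole cluster per arm would go unsampled. That is one way to reach 248. But Protocol 9.1 says that households are drawn from the 64 clusters, and the same total is reached with all 64 represented and a few of them one net short.

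It could also be feared that some households would lose a net without getting one back. Protocol 9.1 ties replacement to each net collected and states no fixed reserve, so that does not follow. The number of nets to set aside is simply left unclear.

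**Conclusion.** Wrong as written. The per-cluster rule, the cluster count and the totals in Protocol 9.1 cannot all be followed. As the text stands, four per cluster in 64 clusters gives 256 households per survey and 128 nets per arm; the stated figures are lower by 8 and 4, about 3%.

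The contradiction itself rests on no assumption beyond the stated inputs. That 256 and 128 are the right replacements assumes that four per cluster in every cluster is the intention, which is what the sentence says but which no other text confirms. The totals may have been worked out for 62 clusters; the documents do not say so.

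The consequence is minor. It is confined to a secondary assessment that depends on funding, and has no effect on the primary outcome or its power.

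**What to change.** Decide which element of Protocol 9.1 governs, and make the others agree with it.

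- **If four per cluster in all 64 clusters is meant:** change 248 to 256, 124 per arm to 128, and 124 nets of each type to 128. Set aside replacement nets to match. The cost is three corrected figures, and 8 more nets withdrawn and replaced per survey (4 of each type), or 16 over two surveys.
- **If 248 is a fixed limit:** remove the flat four-per-cluster statement and name, before collection starts, the clusters that contribute fewer, in equal numbers by arm. The 56-and-8 split shown above is one arrangement that does this. The cost is a sentence and a short list, with no extra nets.

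Neither option calls for a change to the SAP or to the primary analysis.
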